The signature below constitutes the approval of this protocol and the attachments, and provides the necessary assurances that this trial will be conducted according to all stipulations of the protocol, including all statements regarding confidentiality, and according to local legal and regulatory requirements and applicable US federal regulations and ICH guidelines.

Principal Investigator: [name] Department of Ob and Gyn Columbia University Medical center	(signature)	(date: DD-MMM-YYYY)
Co-Investigator: [name] Department of Ob and Gyn University of Texas Medical Branch	(signature)	(date: DD-MMM-YYYY)

PROTOCOL SYNOPSIS PAGE

Background - In developed nations 25 % of pregnant women undergo induction of labor (IOL) for various indications. Likelihood of vaginal delivery depends on the degree of ripeness of cervix. Majority of women undergoing induction of labor are candidates for cervical ripening. Dilapan-S[®] is an osmotic hygroscopic dilator of cervix commonly used for cervical preparation for mid trimester abortions. It has been proven safe for use for IOL at term. Misoprostol is a synthetic prostaglandin E1 analogue, widely used for cervical ripening and IOL in United States and is considered as standard of care.

Objective - To assess the efficacy of Dilapan-S[®] for cervical ripening compared to Misoprostol in women undergoing IOL at or more than 37 weeks gestation.

Primary outcome - Proportion of women randomized to receive Dilapan-S[®] and Misoprostol for cervical ripening achieving vaginal delivery within 36 hours of intervention.

Secondary outcomes - A composite of maternal and fetal outcomes including overall vaginal delivery rate, cesarean section rate, Bishop score after cervical ripening, infections, postpartum hemorrhage. Neonatal outcomes include Apgar scores, NICU admission and sepsis.

Study design - Non Inferiority, unblinded randomized, controlled trial where 322 eligible participants undergoing IOL at >37 weeks gestation at CUMC and admitted to labor and delivery unit will be enrolled and randomly assigned in a ratio 1:1 to either receive Dilapan-S[®] or Misoprostol for cervical ripening. The study is powered at 85% for detecting the primary outcome with a type 1 error at 2.5% for one-sided test.

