Non-inferiority unblinded randomized controlled trial where subjects will be randomized in a ratio of 1:1 to Dilapan-S[®] and misoprostol groups. We decided to use the non-inferiority design as Misoprostol is considered as one of the accepted and standard treatments for induction of labor in United States. Our assumptions for the trial are based on results of PROBAAT-II trial, a large well designed randomized trial conducted in EU for studying efficacy of mechanical and pharmacological methods for labor induction. Assuming a rate of vaginal delivery within 36 hours to be 65% for Misoprostol and 71% for mechanical method (based on data on transcervical Foley catheter in PROBAAT-II [3] and a recent trial comparing Foley catheter to Dilapan-S[®] for cervical ripening done by Saad et al. [12]), with a non-inferiority margin of 10 % and an expected screen failures rate of 5%, a total of 322 subjects will need to be randomized in ratio 1:1 to Dilapan-S[®] vs Misoprostol group. 153 eligible and assessable subjects are needed in Dilapan-S[®] group and 153 in Misoprostol group for analysis. The study is powered at 85% for detecting the primary outcome with a type 1 error at 2.5% for one-sided test.

Objective for the trial

To assess efficacy of cervical ripening with Dilapan-S[®] or Misoprostol in women undergoing induction of labor.

Primary research question (primary endpoint)

Proportion of subjects achieving vaginal delivery within 36 hours after the initiation of the cervical ripening in Misoprostol and Dilapan-S[®] group.

Rationale: The authors of PROBAAT-II study make the valid point that as an outcome of labor induction, giving birth vaginally is more important than how quickly it happens; therefore 24 hours may not be a long enough time for appropriate assessment. Indeed, the effect found in the PROBAAT-II study would have been reversed had the outcome been measured by assessing vaginal delivery within 36 hours. There is therefore a call to standardize the outcome measure in IOL trials to a vaginal delivery within 36 hours [6], particularly when mechanical methods are employed.

Secondary research questions (secondary endpoints)

- Bishop score at 12 hours after the intervention
- Percentage of subjects delivering vaginally in 24 hours after the initiation of intervention
- Overall vaginal delivery rate in each group
- Rate of operative deliveries
- Rate of cesarean deliveries in each group.
- Total length of hospital stay

Maternal outcomes:

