### 6.1.1. MEASURES TO ADJUST FOR MULTIPLICITY, CONFOUNDERS AND HETEROGENEITY

Only one primary objective, outcome and pair of hypotheses is set. Subgroup/Covariate analyses will be introduced as sensitivity analysis if appropriate.

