#### 7.2. ANALYSIS OF THE PRIMARY ENDPOINT

The primary outcome is the proportion of subjects achieving vaginal delivery within 36 hours after the initiation of the cervical ripening in Misoprostol and Dilapan-S® groups. Proportion of patients in each group and their difference will be calculated. One-sided 97.5% confidence interval adjusted for the stratification factors (parity and gestational age) will be calculated for the difference in the proportions and conclusion about non-inferiority will be drawn from it taking into consideration a 10% non-inferiority margin. Unadjusted confidence interval will be calculated as well.

Additionally, the primary outcome will be analysed for each stratification factor. Mantel-Haenszel test will be used to test the difference between the subgroups.

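### The primary interval is valid as written, but leaves the pre-randomisation Bishop score unused; adjusting for it would give a small gain in precision at almost no cost

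*SAP*

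**What the plan says.** SAP 7.2 and the protocol's section on evaluating the primary variable agree. The one-sided 97.5% interval for the difference in vaginal delivery within 36 hours is "adjusted for the stratification factors (parity and gestational age) will be calculated for the difference in the proportions", and an unadjusted interval is also given. These two factors are the randomisation strata, with gestational age split at 39 weeks. SAP 6.1.1 adds that "Subgroup/Covariate analyses will be introduced as sensitivity analysis if appropriate", without naming a covariate.

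On the cervix, the protocol synopsis (Background) says "Likelihood of vaginal delivery depends on the degree of ripeness of cervix". The protocol's Background section calls a Bishop score of 6 or more a good predictor of vaginal delivery within 24 hours. A score of 6 or more is an exclusion criterion, so every woman needs a score before randomisation. SAP 3.2 lists change in Bishop score as a secondary endpoint, which implies a baseline value in both arms.

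Two details matter for using the score. The synopsis (Procedures) and SAP 2 describe a Bishop assessment after randomisation. Recording of the eligibility score is written out only under Arm A in the protocol's Pre-induction section.

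**The concern.** When a baseline variable predicts the outcome and is already being assessed, adjusting for it shortens the confidence interval without enrolling anyone else. Here the decision turns on whether a lower limit clears a 10-point margin, and the planned half-width is itself about 10 points, so small gains in precision have some value. Bishop score is a natural candidate: the protocol links cervical ripeness to the outcome, and the trial already has to assess the score. What is at stake is available precision that the plan does not use.

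**Working it through.** **Inputs from the documents (Protocol, Study Design).** "Assuming a rate of vaginal delivery within 36 hours to be 65% for Misoprostol and 71% for mechanical method"; margin 10 points; "The study is powered at 85% for detecting the primary outcome with a type 1 error at 2.5% for one-sided test"; "153 eligible and assessable subjects are needed" per arm.

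**Step 1: reproduce the plan.** With unpooled variance,

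n per arm = (1.960 + 1.036)² × (0.65 × 0.35 + 0.71 × 0.29) / (0.10 + 0.06)² = 8.978 × 0.4334 / 0.0256 = 152.0,

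which rounds up to 153 because the unrounded value is 152.001. Then 306 × 1.05 = 321.3, giving 322 randomised. At 153 per arm, SE = √(0.4334 / 153) = 5.32 points, half-width = 1.96 × 5.32 = 10.43 points, and power = Φ(0.16 / 0.0532 − 1.96) = Φ(1.046) = 85.2%. The plan's figure is reproduced with no credit for any covariate.

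**Step 2: share of variance that Bishop score could explain.** Nothing in the documents gives this, so the following are assumptions:

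- overall rate 68% (the mid-point of 65% and 71%);
- 60% nulliparous, and an odds ratio of 3 for parity;
- Bishop score between 0 and 5, with standard deviation 1.2 (probabilities 0.03, 0.10, 0.30, 0.32, 0.17, 0.08) or 1.5 (0.08, 0.15, 0.22, 0.22, 0.18, 0.15);
- a logistic model with parity and a linear Bishop term. Gestational age was not modelled.

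R² = (share explained by parity and Bishop − share explained by parity) / (1 − share explained by parity). For an odds ratio of 1.5 per point and SD 1.5, this is (0.1163 − 0.0476) / (1 − 0.0476) = 7.2%. Over the range:

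| Odds ratio per point | R², SD 1.2 | R², SD 1.5 |
|---|---|---|
| 1.1 | 0.3% | 0.4% |
| 1.2 | 1.0% | 1.6% |
| 1.3 | 2.0% | 3.2% |
| 1.5 | 4.5% | 7.2% |

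Letting parous women have somewhat higher scores barely changed these values.

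**Step 3: effect on the primary interval.** Multiply the variance by (1 − R²), with 153 per arm and 65% versus 71%:

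| R² | Power | Half-width (points) | Equivalent women per arm (152 × R²) |
|---|---|---|---|
| 0 | 85.2% | 10.43 | 0 |
| 0.3% | 85.3% | 10.42 | 0.5 |
| 1.0% | 85.6% | 10.38 | 1.5 |
| 4.5% | 86.8% | 10.19 | 6.8 |
| 7.2% | 87.7% | 10.05 | 10.9 |

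The starting row takes no credit for the strata adjustment either. The table therefore shows the size of the gain, not the absolute power of the planned analysis.

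**Step 4: is chance imbalance a further problem?** A one-SD chance difference in mean Bishop score between arms is 1.3 × √(2 / 153) = 0.149 points. The slope is roughly ln(odds ratio) × 0.68 × 0.32, or 4.0 to 8.8 percentage points per Bishop point for odds ratios of 1.2 to 1.5. The resulting shift is 0.59 to 1.31 points. As a share of the sampling variance this is (0.59 / 5.32)² = 1.2% to (1.31 / 5.32)² = 6.1%. That is the same variance component as R² in step 2, seen from another side, and the standard error already contains it.

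**The case against.** The strongest reply is that the plan contains no error. It adjusts for both stratification factors, adds an unadjusted interval, and meets its power without help from any covariate. Leaving out one more prognostic variable neither biases a randomised comparison nor invalidates the one-sided limit. That stands in full.

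Four stronger readings are tempting, and the documents do not support them.

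- *The protocol calls Bishop score the determinant of vaginal delivery.* It says that likelihood depends on ripeness. Its one statement about the score as a predictor concerns values of 6 or more and delivery within 24 hours, whereas enrolled women score below 6 and the endpoint is at 36 hours.
- *A chance imbalance in Bishop score threatens the decision beyond the loss of precision.* Step 4 shows that this would count the same variance twice.
- *SAP 6.1.1 allows the primary covariates to be chosen after the data are seen.* That sentence concerns sensitivity analyses. The covariates of the primary interval are fixed in SAP 7.2.
- *The trial is underpowered because the score is omitted.* Step 1 gives 85.2% without it.

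It is also fair to say that the gain is not wholly free. The eligibility score is explicitly recorded only under Arm A, and a model-based interval would replace a simpler stratified one. These points call for care in the wording but do not remove the benefit.

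**Conclusion.** The point holds as a minor, optional improvement. The primary interval is valid, but it leaves out a likely prognostic variable that the trial already assesses. For odds ratios of 1.1 to 1.5 per Bishop point the gain is about 0.1 to 2.5 points of power and 0.02 to 0.4 points of half-width, worth at most about 11 women per arm. The range rests on the assumed odds ratios, Bishop distributions and parity effect. An odds ratio below 1.1 would make the gain negligible. The adjustment would not protect the trial if the assumed 6-point advantage for Dilapan-S is absent: at 65% in both arms power is 45.0%, and even R² of 10% raises it only to 48.9%.

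**What to change.** Before database lock, amend SAP 7.2 as follows.

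1. Estimate the primary risk difference by standardisation (g-computation) from a logistic model with arm, parity, gestational-age stratum and eligibility Bishop score. Take a robust or bootstrap one-sided 97.5% limit and compare it with the 10-point margin. The result is a marginal risk difference, so the margin keeps its meaning.
2. State that the score is the one taken for eligibility before randomisation. The assessment described after randomisation in the synopsis and SAP 2 should not be used, because in an open-label trial it could be influenced by knowledge of the arm.
3. State that the eligibility score is recorded in both arms, and give a simple rule, blind to arm, for any missing value.
4. Keep the strata-only and unadjusted intervals as supporting analyses.

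The cost is a paragraph of SAP text and short code, with light dependence on a working model that the strata-only interval checks. If outcomes by arm have already been seen, the primary analysis should stay as it is, and the adjusted estimate should be reported as supporting only.

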#### 7.3. ANALYSIS OF SECONDARY ENDPOINTS

All quantitative secondary variables will be summarized separately for each arm. Means of the two treatment arms will be compared with two-sample t-test and Wilcoxon rank-sum test as appropriate.

All secondary variables involving rates and percentages, will be calculated for both arms. Difference in proportions will be derived together with a 95% two-sided confidence interval. The difference between treatment groups will be concluded if the confidence interval does not include zero.

Maternal and neonatal outcomes will be summarized as reported in the CRF.

Delivery time will be presented using Kaplan-Meier curves with censoring for caesarean delivery.

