Participating providers at Columbia University Medical Center will watch a video tutorial on insertion as part of their training and perform at least one Dilapan-S[®] insertion for patients undergoing induction of labor, prior to initiation of the trial. These will not be study participants and no data will be collected in these women. This will be done in the presence of the PI or other trained providers. The purpose of this training is to ensure that all participating providers follow the Dilapan-S[®] Instructions for use as per the manufacturer's recommendation based on FDA approval for its use for cervical ripening. This will be documented in Training Log placed in Regulatory binder.

Participating providers at UTMB regularly perform Dilapan-S® insertion for patients undergoing induction of labor per standard of care, however any provider that has not previously performed Dilapan-S® insertion will watch a video tutorial on insertion as part of their training and perform at least one Dilapan-S® insertion for patients undergoing induction of labor, prior to placing Dilapan-S® for research study purposes. These will not be study participants and no data will be collected in these women. This will be done in the presence of the PI or other trained providers. The purpose of this training is to ensure that all participating providers follow the Dilapan-S® Instructions for use as per the manufacturer's recommendation based on FDA approval for its use for cervical ripening. This will be documented in Training Log placed in Regulatory binder

Study Procedures

Screening for Eligibility and Consent

All women admitted to labor and delivery at initiated sites within Columbia University Medical Center and at UTMB for induction of labor will be screened for eligibility for participation by trained research staff. Women who meet the criteria for inclusion in the trial will be assessed by the Attending physician, Resident or Midwife providing care to the patient and informed about the trial and they are candidates for cervical ripening. Patients who agree to participate in the trial will be required to sign and date an Informed Consent Form (ICF).

Randomization

Participants will be randomized in a ratio of 1:1 for Dilapan-S[®] insertion or oral Misoprostol, using stratification for:

- (A) parity (nulliparous vs. parous women) and
- (B) gestational age (≤39 weeks vs. >39 weeks).
- Due to the nature of intervention blinding of subjects or providers is not possible.

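### SAP 7.3 specifies no adjustment for the randomisation strata in the secondary delivery proportions; read as crude, those intervals are valid but somewhat too wide

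*SAP*

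**What the plan says.** The protocol (Randomization) stratifies 1:1 allocation on "A) parity (nulliparous vs. parous women) and" gestational age, split at 39 weeks. For the 36-hour primary endpoint, SAP 7.2 plans a one-sided 97.5% interval "adjusted for the stratification factors (parity and gestational age) will be calculated for the difference in the proportions", and adds that an unadjusted interval will be produced too. The protocol (Evaluation of the primary variable) says the same.

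For every secondary rate, SAP 7.3 and the protocol (Evaluation of the secondary variables) share one sentence: "Difference in proportions will be derived together with a 95% two-sided confidence interval". A treatment difference is then declared if zero lies outside the interval. Neither place says whether the interval is adjusted. The only general statement on covariates, SAP 6.1.1, allows subgroup or covariate analyses as a sensitivity analysis where appropriate, and names no endpoint.

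**The concern.** When allocation is balanced within strata of a prognostic factor, the design removes the between-stratum part of the variance from the treatment comparison. A crude interval still counts that part, so it is wider than the design warrants. Parity is a stratification factor here and plausibly predicts mode and timing of delivery. The outcomes affected (vaginal delivery within 24 hours, overall vaginal delivery, caesarean and operative delivery) are the main support for the primary result, and their intervals carry a decision rule. At stake is a somewhat lower chance of declaring a true difference on these outcomes, from a choice that the plan leaves unstated.

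**Working it through.** **1. The plan's own figure.** Inputs are from the protocol, Study Design: "Assuming a rate of vaginal delivery within 36 hours to be 65% for Misoprostol and 71% for mechanical method"; "with a non-inferiority margin of 10 % and an expected screen failures rate of 5" per cent; "The study is powered at 85% for detecting the primary outcome with a type 1 error at 2.5% for one-sided test". With unpooled variance:

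n per arm = (0.65×0.35 + 0.71×0.29) × (1.960 + 1.036)² / (0.71 − 0.65 + 0.10)² = 0.4334 × 8.98 / 0.0256 ≈ 152.0, just above 152, so 153 after rounding up. Power at 153 is 85.2%.

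This matches "153 eligible and assessable subjects are needed in" each arm. Then 306/0.95 = 322.1 and 306×1.05 = 321.3, both consistent with "a total of 322 subjects will need to be randomized in ratio 1:1". The documents give no precision figure for the secondary proportions, so there is none to reproduce.

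**2. Formula.** Let f be the nulliparous share, g the gap in event rate between parity groups, and p the overall rate. Then

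p(1−p) = average within-stratum variance + f(1−f)g².

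The crude half-width is 1.96 × √[2p(1−p)/n]. The parity-adjusted half-width (Mantel-Haenszel weights) uses only the within-stratum term. The proportional narrowing, 1 − √{1 − f(1−f)g²/[p(1−p)]}, does not depend on n.

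**3. Half-widths.** The values of f and g are assumptions, because the documents give neither. The overall rate is set at 65%, borrowed from the misoprostol planning rate at 36 hours. With f = 0.6 and n = 153 per arm, p(1−p) = 0.2275:

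| Parity gap (points) | f(1−f)g² | Within-stratum variance | Crude half-width (points) | Adjusted half-width (points) | Narrower by |
|---|---|---|---|---|---|
| 10 | 0.0024 | 0.2251 | 10.69 | 10.63 | 0.5% |
| 20 | 0.0096 | 0.2179 | 10.69 | 10.46 | 2.1% |
| 30 | 0.0216 | 0.2059 | 10.69 | 10.17 | 4.9% |
| 40 | 0.0384 | 0.1891 | 10.69 | 9.74 | 8.8% |

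Varying f from 0.4 to 0.7, and the pair of rates as well, gives about 0.5%, 2%, 4–5% and 7–9%. With no parity effect the gain is zero.

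**4. Caesarean.** Assume half the women are nulliparous, caesarean rates of 35% and 8% by parity, and 161 per arm (322/2, since ITT is the primary efficacy population). Then p = 0.215, p(1−p) = 0.1688, and the within-stratum variance is (0.2275 + 0.0736)/2 = 0.1506, a ratio of 0.892. The half-width falls from 8.97 to 8.48 points. At 25% v 10% the variance ratio is 0.961 (2% narrower); at 40% v 5% it is 0.824 (9% narrower).

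**5. Simulation.** 40,000 trials per scenario, 153 per arm, 1:1 within parity strata. Coverage and SD are under no difference; the last column is the chance of excluding zero when the true difference is 10 points.

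| Nulliparous share; rates in nulliparous / parous | SD of estimate, crude / adjusted (points) | Coverage, crude / adjusted | Excludes zero, crude / adjusted |
|---|---|---|---|
| 60%; 60% / 70% | 5.44 / 5.44 | 95.1% / 95.0% | 44.9% / 45.2% |
| 60%; 55% / 75% | 5.38 / 5.38 | 95.3% / 94.8% | 45.2% / 46.4% |
| 60%; 50% / 80% | 5.30 / 5.30 | 95.8% / 94.7% | 44.6% / 47.8% |
| 60%; 40% / 80% | 5.16 / 5.16 | 96.5% / 95.0% | 44.6% / 49.6% |
| 50%; 45% / 85% | 4.95 / 4.95 | 96.9% / 94.7% | 46.3% / 53.9% |

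The two estimates vary equally; only the reported interval differs. In the third row, 1.96 × 5.30 = 10.39 points is the width the estimate deserves. The crude interval reports 10.84 and the adjusted one 10.30. The simple adjusted interval is sometimes slightly short of 95% coverage, so a small part of its gain in power comes from that.

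**The case against.** Much of the case on the other side stands.

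- **The plan does not say crude.** A reader might infer that SAP 7.3 prescribes unadjusted intervals. It is silent. Crude is the natural reading, because SAP 7.2 names both kinds of interval where each is meant, but it remains an inference.
- **Information is not thrown away.** A reader might infer that precision is lost, or convert the narrowing into an equivalent number of extra women. Stratified randomisation has already delivered the balance, and the estimate has practically the same sampling SD either way. The crude interval over-covers, which errs against false claims of difference.
- **The 24-hour and 36-hour results can still be compared.** A reader might infer that they would stand on different methods. SAP 7.2 also plans an unadjusted 36-hour interval, so a like-for-like crude comparison exists. What is missing is a 24-hour counterpart to the adjusted primary result.
- **The effect is small and the endpoints are secondary.** The trial is sized only for the primary endpoint. In the scenarios tried, a crude interval excludes zero only about 45% of the time for a true 10-point difference. Adjustment adds 0.3, 1.2 and 3.2 percentage points at parity gaps of 10, 20 and 30.

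Plain differences for secondary endpoints are therefore a defensible choice. What this does not answer is why the analysis should ignore strata that the design uses, when the adjusted method is already planned for the primary endpoint and the choice is otherwise left open in an unblinded trial.

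**Conclusion.** The point holds as a low-priority improvement. Neither document specifies adjustment for the stratification factors in the secondary delivery proportions. If the intervals are crude, they are valid but conservative to the extent that parity predicts the outcome: about 5% of half-width or less for parity gaps up to 30 points, and 7–9% at 40. Simulated coverage is 95.1–95.8% for gaps of 10 to 30 points and 96.5–96.9% at 40. The documents do not support a claim of an invalid analysis or of a less precise estimate, and the primary non-inferiority conclusion is untouched.

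These sizes rest on an assumed nulliparous share, assumed rates by parity, Mantel-Haenszel weighting and 1:1 balance within strata. Gestational age, the second stratification factor, was left out of the calculation, so its contribution is not quantified.

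**What to change.** Add to SAP 7.3: *Differences in 24-hour vaginal delivery, overall vaginal delivery, caesarean and operative delivery rates are estimated with the same parity- and gestational-age-stratified 95% interval as the primary endpoint. The unadjusted interval is shown as supportive. For rare outcomes, unadjusted score or exact intervals are used.*

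The last sentence matters because strata would be sparse for rare maternal and neonatal events. The protocol leaves analytic detail to the SAP, so the SAP is the place for the change. The cost is a few lines of text and reuse of the primary-endpoint program, with no extra data and no effect on sample size.

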To ensure safety of the subjects, local monitoring will be completed by the Quality Assurance Monitor for the Department of Obstetrics and Gynecology for this Investigator/Peer study. At each scheduled monitoring visit, the QA will randomly select a representative number of study subject charts to be reviewed. Additional monitoring will be based on the initial monitoring review. An independent monitor appointed by the Funder {Medicem} will review the data periodically throughout the duration of trial to ensure the subject safety, data quality and protocol compliance.

Biostatistics

Primary/Null Hypothesis, to be rejected is as follows: Dilapan is inferior to Misoprostol in efficacy for cervical ripening for induction of labor.

Basic principles for an evaluation of the study are presented in this section. It is concerned mostly about the study populations and evaluation of the study endpoints, more detailed

Version 3.1 dated SEP 4, 2020

COMRED

description of how to analyze collected data will be specified in statistical analysis plan (SAP) which will be written and approved before the database lock.

Additionally, the primary outcome will be analyzed on each stratification factor. Mantel-Haenzsel test will be used to test the difference between the subgroups. This testing will be done for exploratory purposes only.

Study populations

Safety Population

The Safety population will be comprised of all subjects to whom Dilapan-S[®] was inserted or who received at least one dose of misoprostol. This population will be based on the actual treatment received if this differs from that to which the subject was randomized. This population will be used for the analysis of safety data.

Intent-to-treat Population (ITT)

ITT includes all patients that were randomized into the study. ITT subjects will be analyzed in accordance with their randomized study treatment (i.e. in the treatment group they were originally allocated, regardless of treatment actually received). ITT will be used for evaluation of the baseline characteristics and as the primary population for efficacy assessments.

Per Protocol Population (PP)

PP is a subset of ITT patients who received study treatment. Following patients will be excluded from the PP population:

- 1. Patients with major protocol violation affecting the efficacy endpoints. Major protocol violations include (but are not limited to): a. Treatment assignment error
 - b. Violation of one or more inclusion/exclusion criteria

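### The plan concludes a treatment difference from each unadjusted 95% interval for 4 to 13 secondary proportions, with no multiplicity control and no descriptive label

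*SAP*

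**What the plan says.** SAP 7.3 treats secondary endpoints in separate statements.

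- **Rates and percentages.** These are computed in each arm and compared by interval: "Difference in proportions will be derived together with a 95% two-sided confidence interval". Then comes the rule: "The difference between treatment groups will be concluded if the confidence interval does not include zero". The protocol's Evaluation of the secondary variables contains the same rule.
- **Quantitative variables.** "Means of the two treatment arms will be compared with two-sample t-test and Wilcoxon rank-sum test as appropriate". No rule for drawing a conclusion is attached, but SAP 6.1 sets a 5% significance level for statistical analyses in general.
- **Maternal and neonatal outcomes.** "Maternal and neonatal outcomes will be summarized as reported in the CRF". The protocol says the same.

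On multiplicity, SAP 6.1.1 says "Only one primary objective, outcome and pair of hypotheses is set" and adds that subgroup or covariate analyses may serve as sensitivity analyses. It does not mention the secondary endpoints.

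For the analyses of the primary outcome by stratification factor, the protocol's Biostatistics section says "This testing will be done for exploratory purposes only". SAP 7.2 keeps the test ("Mantel-Haenszel test will be used to test the difference between the subgroups") without that limit.

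**The concern.** Unadjusted intervals for secondary endpoints are ordinary when they are offered as description. This plan goes further and commits the report to concluding a difference whenever an interval excludes zero. Having one primary hypothesis protects the primary claim. It does not protect conclusions drawn separately on several other endpoints, each carrying a 5% error of its own.

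A report that follows the plan could therefore state a difference in delivery mode or timing as a finding when it is chance. If the rule reaches that far, the same holds for maternal or neonatal outcomes. The rule also invites the reverse error of reading an interval that contains zero as no difference, which matters most for rare safety outcomes.

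**Working it through.** **The plan's own figure.** The documents give no familywise error rate for secondary endpoints. The only error control they quantify is for the primary test: 65% against 71%, a 10-point margin, one-sided 2.5% and 85% power (protocol, Study Design). With distance 0.71 − 0.65 + 0.10 = 0.16 and variance term 0.65×0.35 + 0.71×0.29 = 0.4334:

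n per arm = 0.4334 × (1.960 + 1.036)² / 0.16² = 152.001, rounded up to 153.

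This matches the stated 153, with 85.2% power at that size. The 2.5% belongs wholly to the primary test and says nothing about the secondary conclusions.

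**Counting the comparisons (SAP 3.2).** Splitting the bullets that hold two variables gives 23. Two exist in one arm only (incomplete misoprostol dosing and failed Dilapan-S insertion), which leaves 21:

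| Type | Variables | Number |
|---|---|---|
| Binary, delivery | vaginal within 24 h, overall vaginal, caesarean, operative | 4 |
| Binary, maternal | chorioamnionitis, endometritis, haemorrhage, severe lacerations | 4 |
| Binary, neonatal | Apgar, pH threshold, base-excess threshold, NICU admission, antibiotics | 5 |
| Quantitative | Bishop score and its change, delivery time, ripening to delivery, oxytocin to delivery, length of stay, cord pH, base excess | 8 |

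The interval rule applies to rates and percentages only. Its reach is therefore 4 + 4 + 5 = 13 at most, or 4 if the separate sentence on maternal and neonatal outcomes takes them out. The composites mentioned at the head of SAP 3.2 are not listed as endpoints and are not counted.

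**Chance of at least one false conclusion**, all nulls true, 5% per comparison, independent: 1 − 0.95^k.

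- k = 4: 1 − 0.95⁴ = 18.5%
- k = 13: 1 − 0.95¹³ = 48.7%
- k = 3, because the caesarean rate is the complement of overall vaginal delivery: 1 − 0.95³ = 14.3%

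**Correlation (assumed; the documents give none).** Simulating normal statistics with a common correlation of 0.3 or 0.5 gives 17.5% or 15.6% for k = 4, and 41.9% or 33.3% for k = 13.

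**Rare outcomes (assumed rates).** With 322/2 = 161 per arm and a Wald interval (also assumed, since the SAP names no method), a true rate of 0.5% gives a false exclusion of zero 0.8% of the time, and a rate of 1% gives 3.2%. From 2% to 65% the figure is 4.5% to 5.3%. Rare maternal and neonatal events therefore contribute less than 5% each, which lowers the k = 13 figure further.

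**Adding the quantitative tests.** If maternal and neonatal outcomes are only summarized, cord pH and base excess drop out too. That leaves 4 + 6 = 10 comparisons, and 1 − 0.95¹⁰ = 40.1%. This is the chance of any nominally significant result, not of a conclusion under the interval rule.

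**The case against.** The strongest reply has four parts.

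First, the rule may be narrow. Both documents give maternal and neonatal outcomes their own sentence saying that they are summarized. The SAP's list of efficacy tables makes the same split: Tables 14.2.2.2 and 14.2.3.1 are analyses of proportions, while 14.2.6.1 and 14.2.7.1 are summary statistics. This stands as a reasonable reading and is why the lower figure is given. It is not conclusive, because the rule is framed for all secondary rates and SAP 3.2 lists these outcomes as secondary endpoints.

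Second, a reader might count all 21 between-arm variables, obtain 1 − 0.95²¹ = 65.9%, and infer that at least one false claim is more likely than not. The documents do not support that. Eight of the 21 are quantitative and fall outside the rule. Independence also fails: two delivery rates are complements, and pH and base excess each appear as both a mean and a threshold. No reading of the rule reaches 50%, which would need 14 independent comparisons (51.2%).

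Third, one primary hypothesis is set, and nothing in either document makes a secondary result a basis for trial success. This is correct and limits the consequence. It does not remove a written instruction to conclude.

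Fourth, the missing exploratory label in SAP 7.2 does not revoke the protocol's, and no decision rule is attached to that test. This also stands, so it is a minor matter of consistency. A reader should not infer that the SAP has made the subgroup tests confirmatory.

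**Conclusion.** The concern holds for the interval rule. Followed as written, the plan draws conclusions on 4 to 13 secondary proportions with no error control across them. The chance of at least one false conclusion is about 19% to 49%, assuming that no true differences exist, that each comparison has 5% error and that they are independent. Overlap between endpoints and rare events reduce this, to roughly 14% to 18% for the four delivery rates under the assumptions tried. Even the low end is well above 5%.

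The 6 to 8 quantitative tests are also unadjusted, but the plan does not say that a difference is concluded from them. The primary non-inferiority test, its margin and its error rate are unaffected. This should be corrected, but it does not threaten the trial's main result.

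**What to change.** Replace the rule in both SAP 7.3 and the protocol's Evaluation of the secondary variables; changing only one would put the two documents in conflict. Suggested text:

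*Secondary endpoints are reported as estimates with unadjusted 95% intervals (differences in means or proportions); these intervals and any t-test or Wilcoxon p-values are descriptive, and no confirmatory conclusion of a difference, or of no difference, is drawn from them.*

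State that this covers maternal and neonatal outcomes, which settles the open question about the rule's reach. In SAP 7.2, carry over the protocol's exploratory label for the analyses by stratification factor.

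The cost is wording in two documents, plus intervals for differences in means, which SAP 7.3 does not now provide. No power is lost on the primary test. The small downside is that no formal secondary claims can be made. If such claims are wanted, the alternative is to name the endpoints and adjust. Bonferroni would need 98.75% intervals for 4 comparisons (0.05/4 = 0.0125) or 99.62% for 13 (0.05/13 = 0.00385).
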